05/09/2019	
1. Secondary Objectives
 
Section 2.2.8 Fingerstick Test
 
95% of glucose results shall fall within $\pm 12.5\text{mg/dL}$ of laboratory method at glucose concentrations $<100\text{ mg/dL}$ and within $\pm 12.5\%$ at glucose concentrations $\geq 100\text{ mg/dL}^{**}$ 
CHANGED TO
 
Test the hypothesis that there is at least a 95% probability that meter results would be within $\pm 12.5\text{mg/dL}$ of laboratory method at glucose concentrations $<100\text{ mg/dL}$ and within $\pm 12.5\%$ at glucose concentrations $\geq 100\text{ mg/dL}^{**}$ 
2. Secondary Objectives
 
Section 2.2.9 Study Staff Test
 
95% of glucose results shall fall within $\pm 15\text{mg/dL}$ of laboratory method at glucose concentrations $<100\text{ mg/dL}$ and within $\pm 15\%$ at glucose concentrations $\geq 100\text{ mg/dL}^{**}$ 
CHANGED TO
 
Test the hypothesis that there is at least a 95% probability that meter results would be within $\pm 15\text{mg/dL}$ of laboratory method at glucose concentrations $<100\text{ mg/dL}$ and within $\pm 15\%$ at glucose concentrations $\geq 100\text{ mg/dL}^{**}$ 
3. Section 4.2 Exclusion Criteria
 
Added the following exclusion criteria:
 
Being in this trial during or soon after xylose absorption testing (Xylose in the blood is known to cause interference). However, subjects can be enrolled as soon as 2 days after the test is performed (25 gms of oral xylose administered during this test is cleared within 480 mins or 8 hours). 
4. Removed Section 5.6 Subject Enrolment and merged all information regarding the study enrolment to Section 4.3 Subject Recruitment (the section was previously named as General Enrolment Details).

TABLE OF CONTENTS

1.0 BACKGROUND INFORMATION	6
2.0 STUDY OBJECTIVES	6
3.0 STUDY DESIGN	8
4.0 INCLUSION/EXCLUSION CRITERIA AND SUBJECT RECRUITMENT	10

1.0 Background Information

T-PLUS (Thunder PLUS) is the code name of a blood glucose monitoring system (BGMS) consisting of a new meter and CONTOUR PLUS test strips. The proposed brand name for this BGMS is “Contour Plus BLUE”. This system will be marketed in the US and globally. The meter can wirelessly transmit BG results using Bluetooth® Low Energy technology to the meter mobile application that will be available on specified versions of the iOS and Android mobile platforms.

This clinical trial will assess the performance (accuracy) of the T-PLUS meters by lay users enrolled as subjects in the study, and by health care professionals (also called study staff).

The trial will follow the requirements and procedures described in Draft FDA Guidance on Self-monitoring Blood Glucose Test Systems: 2018 (FDA SMBG:2018)¹ and ISO 15197:2013 International Standard, Section 8². Results will be evaluated and reported for the T-PLUS system according to each of the two standards (FDA and ISO), for a total of two reports.

2.0 Study Objectives

Study objectives 2.1 is in accordance with **ISO 15197:2013, Section 8**, and apply to data collected ONLY from **subjects who have diabetes**.

2.1 Primary Objectives, ISO 15197:2013

2.1.1 Fingerstick Test: Obtain T-PLUS BGMS performance data in the hands of lay users with diabetes using fingerstick capillary blood obtained with Microlet NEXT® lancing device.

- **95% of glucose results shall fall within $\pm 15\text{mg/dL}$ of laboratory method at glucose concentration $<100 \text{ mg/dL}$ and within $\pm 15\%$ at glucose concentrations $\geq 100 \text{ mg/dL}$**

2.2 Secondary Objectives: Failure of any sub objectives listed below does not constitute the failure of the secondary objective.

Study objectives 2.2.1 to 2.2.3 are in accordance with **ISO 15197:2013, Section 8**, and apply to data collected ONLY from **subjects who have diabetes**.

2.2.1 Alternative Site Test (AST): Obtain T-PLUS BGMS performance data in the hands of lay users with diabetes using capillary blood from the palm site obtained with Microlet NEXT lancing device with the AST endcap. Acceptance criteria will be the same as fingerstick 2.1.1.

2.2.2 Venous Blood Test: Obtain T-PLUS BGMS performance data using venous blood from lay users with diabetes. Acceptance criteria will be the same as fingerstick 2.1.1.

¹ Self-Monitoring Blood Glucose Test Systems for Over-the-Counter Use, Draft Guidance for Industry and Food and Drug Administration Staff. Issued 30Nov2018, Food and Drug Administration, USA. (abbreviated FDA SMBG:2018)

² In vitro diagnostic test systems – Requirements for blood-glucose monitoring systems for self-testing in managing diabetes mellitus. Issued 15 May2013, International Organization for Standardization, Switzerland. (abbreviated ISO 15197:2013)

2.2.3 Subject Questionnaire 1: The questionnaire will include statements about the T-PLUS BGMS instructions for use (product labeling) and ease of use of the basic blood testing operations of the meter system. These statements will be given a rating by the subjects with diabetes (1=strongly disagree, 2=disagree, 3=neutral, 4=agree, 5=strongly agree), and frequency distributions will be tabulated. Results will be compared to the following criteria:

- **Acceptance criteria: There must be at least a 90% probability that a user would respond with a score of 3 or higher to statements concerning instructions for use or ease of use.***

Study objectives 2.2.4 to 2.2.7 are in accordance with **FDA SMBG: 2018**, and apply to data collected from ALL subjects (**subjects who are diabetic and Naïve**).

2.2.4 Fingerstick Test: Obtain T-PLUS BGMS performance data in the hands of **lay users with diabetes and naïve users** (without diabetes) from fingerstick capillary blood using Microlet NEXT lancing device.

- **95% of glucose results shall fall within $\pm 15\%$ of laboratory method across the entire tested range**
- **99% of glucose results shall fall within $\pm 20\%$ of laboratory method across the entire tested range**

2.2.5 Alternative Site Test (AST): Obtain T-PLUS BGMS performance data in the hands of **lay users with diabetes and naïve users** (without diabetes) from the palm site using the Microlet NEXT lancing device with the AST endcap. Acceptance criteria will be the same as fingerstick 2.2.4.

2.2.6 Samples will adequately span the claimed measuring range. At least ten unaltered samples with blood glucose concentration at the lower limits of the measuring range (less than 80 mg/dl) and at least ten unaltered samples at the upper limit measuring range (greater than 250 mg/dl) will be obtained for each anatomical site (i.e. fingerstick & palm).

2.2.7 Subject Questionnaire 1: The questionnaire will include statements about the T-PLUS BGMS instructions for use (product labeling) and ease of use of the basic blood testing operations of the meter system. These statements will be given a rating by all of the subjects (1=strongly disagree, 2=disagree, 3=neutral, 4=agree, 5=strongly agree), and frequency distributions will be tabulated. Results will be compared to the following criteria:

- **Acceptance criteria **: There will be no pass/fail criteria for FDA: SMBG 2018**

*This is a “total population” (hypothesis test) requirement for the pool of all subjects with diabetes.

** This is a “total population” (hypothesis test) requirement for the pool of all subjects (naïve and diabetic).

Study objectives 2.2.8 to 2.2.10 below are internal objectives and apply to data collected from all subjects OR subjects who have diabetes, as specified for each objective.

2.2.8 **Fingerstick Test (only subjects with diabetes):** Obtain T-PLUS BGMS performance data in the hands of lay users with diabetes using fingerstick capillary blood obtained with Microlet NEXT lancing device.

- **Test the hypothesis that there is at least a 95% probability that meter results would be within $\pm 12.5\text{mg/dL}$ of laboratory method at glucose concentrations $<100\text{ mg/dL}$ and within $\pm 12.5\%$ at glucose concentrations $\geq 100\text{ mg/dL}^{**}$**

2.2.9 **Study staff test (two analyses: all subjects and for subjects with diabetes):** Obtain T-PLUS BGMS performance data in the hands of trained study staff testing subjects' fingerstick blood obtained with Microlet NEXT lancing device.

- **Test the hypothesis that there is at least a 95% probability that meter results would be within $\pm 15\text{mg/dL}$ of laboratory method at glucose concentrations $<100\text{ mg/dL}$ and within $\pm 15\%$ at glucose concentrations $\geq 100\text{ mg/dL}^{**}$**

2.2.10 **Subject Questionnaire 2 (only subjects with diabetes):** This questionnaire for subjects with diabetes will include statements about user preferences and feedback regarding the features of the T-PLUS BGMS in routine diabetes management. These statements will be given a rating by the subjects (1=strongly disagree, 2=disagree, 3=neutral, 4=agree, 5=strongly agree), and frequency distributions will be tabulated.

- **Acceptance criteria: There are no pass/fail criteria for Questionnaire 2.**

3.0 Study Design Summary

This study is designed to satisfy both the ***FDA SMBG:2018*** and the ***ISO 15197:2013, Section 8*** requirements. Besides different analysis criteria, the main difference between these regulations is that FDA SMBG:2018 requires that both naïve users (people without diabetes) and people with diabetes to be included in the study population. The ISO 15197:2013 standard states that the study population shall only include people with diabetes.

The study will be conducted at minimum of one clinical site and enroll a total of approximately 370 lay users. Ten to fifteen percent (10 - 15%) of the enrolled subjects will be people without diabetes and twenty percent (20%) of subjects enrolled with diabetes will have Type 1 diabetes. At least 70% of subjects will be younger than age 65.

For this study, there must be at least 350 total evaluable fingerstick self-test results and at least 350 total evaluable AST palm self-test results. ISO 15197:2013 criteria requires at least 100 evaluable results each for fingerstick self-test results, AST palm self-test results, study staff performed fingerstick blood and venous blood tests.

In addition, per FDA SMBG:2018, at least 10 unaltered evaluable subject fingerstick and AST palm blood samples will be $< 80\text{ mg/dL}$ and 10 will be $> 250\text{ mg/dL}$ (by capillary YSI assay). Subject enrollment will continue until the required evaluable samples are collected.

The subjects will be 18 years and older. Each subject will make one visit, lasting approximately 1 hour at the clinical site. Study sessions will be conducted by study staff members who have been trained on all aspects of the protocol, the use of the T-PLUS system, data collection, and GCP.

Procedures: All subjects will complete the informed consent process before performing any study procedures.

- **For All Subjects**

Subjects will be assigned to use the T-PLUS meter and randomized to use one of three Contour Plus test strip lots throughout the visit.

The untrained subjects, who have never used the Ascensia Contour TV3 (Thunder V3), and Thunder PLUS meter systems previously, will be sequestered in such a way that they cannot observe or be influenced by the testing technique of other study participants. They will learn to use the T-PLUS meter by reading the User Guide (UG) and Quick Reference Guide (QRG). Each subject will perform one fingerstick self-test using a Microlet NEXT or similar lancing device and the T-PLUS meter. Immediately following the subject self-test, a Tenderlett™ or similar device will be used by the study staff on the subject's finger (preferably the same hand) to collect a capillary sample for testing on the YSI Glucose Analyzer.

Immediately following the Tenderlett lancing, subjects will lance their palm using the Microlet NEXT lancing device (with AST clear endcap) and will perform a self-test using the meter.

Immediately following the AST test, the staff person will perform a fingerstick test on the subject with the Microlet device and the T-PLUS meter.

All subject capillary and AST self-test results and study staff fingerstick results will be compared to YSI results from blood obtained from the Tenderlett fingerstick.

Hematocrit will be measured for all subjects.

All Subjects will then complete a questionnaire (Questionnaire 1) to provide feedback on the meter system and instructions for use (UG and QRG).

- **Additional Procedures for Subjects with Diabetes**

Subjects with diabetes will be given a venipuncture. The venous blood will be tested by the study staff using the T-PLUS system, , and the YSI lab analyzer. The venipuncture may be performed any time after the subject is enrolled (i.e. upon completion of informed consent and passed inclusion/exclusion criteria).

After all self-testing is completed, staff will demonstrate to the subjects with diabetes several features of the meter system that would not necessarily be experienced during the brief accuracy testing. These subjects will be given a second questionnaire (Questionnaire 2) to provide feedback about the new features of the system.

4.0 Inclusion/Exclusion Criteria and Subject Recruitment

4.1 Inclusion Criteria:

- 4.1.1 Males and females, 18 years of age and older
- 4.1.2 Ability to speak, read and understand English. Subjects must demonstrate ability to read a paragraph from the first page of the UG to qualify for the study.
- 4.1.3 Willing to complete all study procedures

4.2 Exclusion Criteria:

- 4.2.1 Hemophilia or any other bleeding disorder
- 4.2.2 Pregnancy (self-reported)
- 4.2.3 Physical, visual or neurological impairments that would make the person unable to perform testing with the BGMS.
- 4.2.4 Previous participation in a blood glucose monitoring study using the Ascensia Contour TV3 or Thunder V3 and Thunder PLUS BGMS.
- 4.2.5 Working for a medical laboratory, hospital or other clinical setting that involves training on or clinical use of blood glucose monitors.
- 4.2.6 Being in this trial during or soon after xylose absorption testing (Xylose in the blood is known to cause interference). However, subjects can be enrolled as soon as 2 days after the test is performed (25 gms of oral xylose administered during this test is cleared within 480 mins or 8 hours).
- 4.2.7 Working for a competitive medical device company, or having an immediate family member or someone who is not a family member but is living within the household of someone who works for such a company.
 - Immediate family members are the subject's parents, spouse, children, and siblings, including the parent's spouse; step-children and adopted children and their spouses.
 - A competitive medical device company is a company that provides a medical device or components of a device that is related to diabetes.

For example, people who are not eligible are those who work for companies that create or manufacture the following (or a company that is in a partnership with a company that provides such devices): lancing devices, blood glucose monitoring systems, continuous glucose monitoring systems, insulin pens, or systems related to the measurement of HbA1c.

People who are eligible are those who work for companies associated with products such as wound dressings, medications or dietary products.

- 4.2.8 A condition, which in the opinion of the investigator or designee, would put the person or study conduct at risk. The reason for exclusion will be clearly documented by investigator or designee on the subject disposition form.

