4.3 Subject Recruitment

4.3.1 The following additional population criteria are study goals with the site recruiting to meet these goals:

1. Enrolment: At least 370 subjects
2. At least 70% of subjects will be younger than age 65.
3. Ten to fifteen % (10-15%) of subjects will be people without diabetes.
4. At least 20% of subjects (with diabetes) will have type 1 diabetes.

4.3.2 There must be at least 350 total evaluable fingerstick self-test results and at least 350 total evaluable AST palm self-test results. ISO 15197:2013 criteria requires at least 100 evaluable results each for fingerstick self-test results, AST palm self-test results, study staff performed fingerstick blood and venous blood tests.

4.3.3 In Addition, per FDA SMBG:2018, at least 10 unaltered evaluable subject fingerstick and AST palm blood samples will be < 80 mg/dL and 10 will be > 250 mg/dL (by capillary YSI assay). Subject enrollment will continue until the required evaluable samples are collected

4.3.4 No laboratory tests (e.g., pregnancy) are required to assure qualification. Subjects' verbal responses will be accepted and recorded on forms which will serve as source documents for the electronic data capture (EDC) system.

4.3.5 The site study staff will perform the following when the subject arrives at the clinical trial site:

1. Complete the informed consent process.
2. Assign a unique number to each subject.

4.3.6 The study staff will document subject demographics (including both screen-failed and enrolled subjects), diabetes history, medical conditions and medications information. Subjects will also be asked when they last ate, took diabetes medications, and performed vigorous exercise.

4.3.7 If the subject does not have diabetes, the outside of the subject folder will be labeled to indicate that venipuncture should NOT be performed.

4.3.8 According to the randomization schedule, subjects will be assigned to use one of three Contour Plus test strip lots (R,B or G) throughout the visit.

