5.6 Tests (See Table 5.1 for test scheme.)

Each subject will be provided with all the materials needed for self-testing during the visit: one T-PLUS meter, a Microlet NEXT or similar lancing device, lancets, Contour PLUS test strips, associated meter UGs and QRGs. The subject will be given time to review the UG and QRG to learn how to use the system but no training will be provided.

The subject will wash his/her hands thoroughly with warm water and soap, rinse and dry well.

5.6.1 *Fingerstick Testing*

1. The subject will perform a fingerstick using the Microlet NEXT lancing device and test his/her blood on T-PLUS meter. The study staff person will record the time and test result of the successful meter test on the appropriate form. For instructions on handling error codes and repeat testing, refer to protocol section 5.9 'Errors'.
2. Immediately, but at least within 5 minutes of the fingerstick self-test, the study staff person will lance the subject's finger (preferably the same hand as above) with a Tenderlett device

in order to collect enough blood for testing on the YSI Analyzer (approx. 200–300 uL). The time of this Tenderlett lancing will be recorded.

3. If adequate blood is not obtained from the Tenderlett lancing, 2 additional Tenderlett lancings are allowed (total of up to 3 Tenderlett lancings). The blood is to be combined into one tube for YSI analysis.
4. The blood sample will be centrifuged as soon as possible after sample collection but not longer than 15 minutes after the meter test. The study staff will record the time of centrifugation.
5. In order to reduce glycolysis of the plasma, it is recommended that the plasma be transferred from the microtainer tube to a micro/dispo tube or similar container, prior to analysis on the YSI Analyzer.
6. The plasma sample will be assayed on the YSI Analyzer: 1 sip = 1 result from black probe and 1 result from white probe. See 5.11.3 for details on testing of plasma samples.
7. Immediately following the YSI test of the subject plasma sample, a serum control close to the level of the subject plasma will be tested. (No re-calibration is required). The serum control test result should be within the range shown in Table 5.2. See 5.11.32 for details.
8. Additional details regarding processing of blood samples for the YSI Analyzer are found in Appendix B.

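### Section 3.0 describes self-testers who have never used the TV3 or Thunder PLUS meters, but exclusion 4.2.4 screens only for past study participation; the two should be reconciled

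*Combined protocol and SAP*

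**What the plan says.** Protocol section 3.0 (Study Design Summary) introduces the people who do the self-tests as "The untrained subjects, who have never used the Ascensia Contour TV3 (Thunder V3), and Thunder PLUS meter systems previously". They are kept apart so that they cannot observe other participants' technique, and they learn the meter from the User Guide and Quick Reference Guide alone. Section 5.6 repeats this: "The subject will be given time to review the UG and QRG to learn how to use the system but no training will be provided".

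Eligibility is set out in section 4. Exclusion 4.2.4 is the only item that names these systems: "Previous participation in a blood glucose monitoring study using the Ascensia Contour TV3 or Thunder V3 and Thunder PLUS BGMS". Exclusion 4.2.5 concerns occupation: "Working for a medical laboratory, hospital or other clinical setting that involves training on or clinical use of blood glucose monitors". Exclusion 4.2.8 lets the investigator exclude a person whose condition would put that person or the study at risk. The inclusion criteria in 4.1 cover age, English and willingness to complete the procedures.

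At enrolment, section 4.3.6 has staff document demographics, "diabetes history, medical conditions and medications information", and when the subject last ate, took diabetes medication and exercised. Previous use of a particular meter is not listed.

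On the test system itself, section 1.0 says "T-PLUS (Thunder PLUS) is the code name of a blood glucose monitoring system (BGMS) consisting of a new meter and CONTOUR PLUS test strips" and "This system will be marketed in the US and globally". Section 9.1 calls the T-Plus meter investigational. Neither document gives the market status of TV3.

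**The concern.** Never having used a system is a stricter condition than never having been in a study of it. Sites enrol on section 4, so a person who had used TV3 outside a study would satisfy every written criterion and still contradict the population in section 3.0.

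The sponsor names TV3 in both places, so the protocol itself treats experience with TV3 as relevant. The untrained self-test feeds the primary ISO fingerstick objective (2.1.1) and the FDA fingerstick objective (2.2.4). Questionnaire 1 is the most directly exposed, because several of its pass/fail statements ask whether the instructions were easy to understand and explained how to run a test. Someone already practised on a system that the sponsor groups with the test meter would plausibly test more accurately and rate the instructions more kindly. Any bias would therefore tend toward passing.

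**Working it through.** **Step 1: does any criterion deliver the population in 3.0?**

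| Text | What it screens | Covers personal use of TV3? |
|---|---|---|
| 3.0 | Describes subjects as never having used the systems | Describes, but is not an eligibility criterion |
| 4.1.1 to 4.1.3 | Age, English, willingness | No |
| 4.2.4 | Previous study participation | No |
| 4.2.5 | Occupational training or clinical use | No |
| 4.2.8 | Investigator's judgement of a risk condition | Not expressly |
| SAP section 11 | Evaluability of results | No prior-use rule |

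The gap is real on the text.

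**Step 2: the wording of 4.2.4.** It joins three names with 'or' and then 'and'. Section 3.0 shows that TV3 and Thunder V3 are one system. The likely sense is exposure to either system, but the sentence can also be read as requiring both.

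**Step 3: which system matters?** Thunder PLUS is new, investigational and to be marketed later. Exposure to it would be expected through studies, which 4.2.4 covers. That leaves TV3, whose availability is not stated.

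**Step 4: the plan's own figures.** SAP Table 1.1 gives, for ISO, n = 315 and Xc = 300. The exact binomial reproduces it:
- P(X ≥ 300 | 315, 0.9679) = 0.9502 (stated 95.02%).
- P(X < 300 | 315, 0.9277) = 0.9495 (stated 94.95%).

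The wording mismatch alters none of these.

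**Step 5: illustration on assumed rates.** Let q be the share of experienced users, 98% their assumed accuracy and p_N the novice accuracy. With a randomly composed sample, p = (1 − q)·p_N + q·0.98, and the pass chance is P(X ≥ 300 | 315, p). The values of q, the 98% and the 93% are assumptions; 96.79% is the plan's Po.

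| q | p if p_N = 0.93 | Pass chance | p if p_N = 0.9679 | Pass chance |
|---|---|---|---|---|
| 0% | 0.930 | 6.8% | 0.9679 | 95.0% |
| 10% | 0.935 | 12.5% | 0.9691 | 96.2% |
| 20% | 0.940 | 21.3% | 0.9703 | 97.2% |
| 30% | 0.945 | 33.7% | 0.9715 | 98.0% |

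The effect depends heavily on where novice accuracy lies. Near the plan's failing value (Pa = 92.77%) the relative change is large. At Po it is at most 3 percentage points over this range (98.0 − 95.0).

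**The case against.** The strongest reply is that the harm needs a fact the documents do not supply. Nothing says that TV3 was sold, used at home or shown in clinics, and the test meter itself was not yet on the market. This stands, and it makes the consequence conditional.

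A second reply is that section 3.0 is itself protocol text, so a site that knowingly enrolled a TV3 user would already depart from it. That is fair, but 4.2.4 does not prompt the site to ask. The gap is in the screening rule; the intended population is already stated.

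A third is that the 'or' and 'and' reading is strained, since TV3 and Thunder V3 are two names for one system. This largely stands: the ambiguity is minor, though the same edit removes it.

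Two stronger readings are tempting and not supported:
- A reader might infer that such users could never be identified afterwards, because the SAP's diabetes-history tables omit the current meter. Those are mock tables that the SAP says may vary, and the diabetes-history form is not in the documents. The most that can be said is that the documents do not show that prior meter use is recorded.
- A reader might take the naïve users of objective 2.2.4 to mean people new to the device. In this protocol the term means people without diabetes. The expectation of no prior use comes from section 3.0, and that of no training from 3.0 and 5.6; neither comes from the objectives.

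**Conclusion.** The point holds as a mismatch between the stated population and the rule that is meant to produce it. Section 3.0 says never used; 4.2.4 excludes only past study participants, in ambiguous wording; no other criterion closes the gap.

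The consequence rests on an assumption that the documents neither confirm nor rule out, namely that TV3 is available outside studies. If it is, TV3 users could enter the untrained self-test and Questionnaire 1, with a bias that would tend to favour passing. If it is not, the effect is nil. The documents do not support the flat statement that experienced home users will be in the sample.

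Nor do they support reading the rise from 7% to 34% as the expected effect. It uses a novice rate close to the plan's failing value; at the plan's Po the same shares move the pass chance only from 95.0% to 98.0%. The shares and the experienced-user rate have no source in the documents. No stated sample size, critical value or power figure is affected.

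**What to change.** Reword 4.2.4 so that it enforces what 3.0 describes, for example: *Any previous use of, or study participation with, the Contour TV3 (Thunder V3) or the Thunder PLUS BGMS.* This also settles the either-or-both ambiguity. Record the answer at screening; section 4.3.4 already accepts and records verbal responses, so no new procedure is needed.

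The cost is a one-line amendment and one screening question. A few volunteers may be screened out. Adding a current-meter field to the SAP listing, or extending the exclusion to training on the systems, would go beyond what 3.0 states and is not needed to reconcile the two sections.
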